CLINICAL PROTOCOL

CTIX-BRI-205

Phase 2, Multi-center, Randomized, Double-blind, Placebo-controlled Study to Evaluate the Efficacy and Safety of Brilacidin Oral Rinse Administered Daily for 7 Weeks in Attenuating Oral Mucositis in Patients with Head and Neck Cancer Receiving Concurrent Chemotherapy and Radiotherapy

Document type:	Clinical Protocol - Amended
Version number:	1.9
Version date:	23 August 2017
NCT number:	NCT02324335

CONFIDENTIALITY STATEMENT

The information provided in this document is strictly confidential. This information may not be used, published or disclosed without prior written approval from Innovation Pharmaceuticals Inc. (formerly Cellceutix Corporation)

PROTOCOL SYNOPSIS

Name of Sponsor/Company: Innovation Pharmaceuticals Inc. (formerly Cellceutix Corporation)
Name of Finished Product: Brilacidin Solution, 50 mg/ml (free base)
Name of Active Ingredient: Brilacidin tetrahydrochloride
Title of Study: Phase 2, Multi-center, Randomized, Double-blind, Placebo-controlled Study to Evaluate the Efficacy and Safety of Brilacidin Oral Rinse Administered Daily for 7 Weeks in Attenuating Oral Mucositis in Patients with Head and Neck Cancer Receiving Concurrent Chemotherapy and Radiotherapy
Study Centers: Approximately 20 sites in the United States will participate in the study
Number of Subjects Planned: Approximately 60 subjects with head and neck cancer receiving concurrent chemotherapy and radiotherapy
Study Duration per subject: Approximately 17 weeks
Phase of Development: 2
Primary Objective(s): 
• To evaluate the efficacy of topically applied brilacidin administered three times daily by oral rinse for approximately 7 weeks (treatment week is defined as a 7-day period, irrespective of the day of the week that the 7-day period begins) compared to placebo in reducing the incidence of severe OM (defined as grade 3 or 4 on the WHO Oral Mucositis scale, WHO Grade ≥ 3) in subjects with head and neck cancer (HNC) receiving concomitant chemoradiation therapy (CRT).• To evaluate the safety and tolerability of topically applied brilacidin administered three times daily by oral rinse for approximately 7 weeks (treatment week is defined as a 7-day period, irrespective of the day of the week that the 7-day period begins).

Secondary Objectives:

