Brilacidin (45 mg/ 15mL WFI) oral rinse tid, or placebo (15mL WFI) oral rinse tid

Efficacy and Safety Endpoints:

Primary Efficacy Endpoint

Incidence of severe OM (WHO Grade ≥ 3) experienced during radiation therapy by subjects with HNC receiving concomitant chemoradiation therapy and a cumulative radiation dose of at least 55 Gy.

Secondary Efficacy Endpoints

- Duration of severe OM (WHO Grade ≥ 3), from initial WHO Grade ≥ 3 during radiation therapy to the first WHO Grade 2 or lower OM assessment during/after radiation therapy.
- Duration of severe OM (WHO Grade ≥ 3), from initial WHO Grade ≥ 3 during radiation therapy to the last WHO Grade ≥ 3 assessment during/after radiation therapy.
- Time to onset of severe OM (WHO Grade ≥ 3).
- Incidence of severe OM (WHO Grade ≥ 3) by cumulative IMRT.

Safety Endpoints

The safety and tolerability of treatment with brilacidin will be assessed through incidence, severity and type of adverse events, including serious adverse events, and changes in clinical laboratory parameters, blood pressure, heart rate, ECOG, and body weight.

Systemic Exposure/Pharmacokinetic Endpoints

Brilacidin systemic exposure will be estimated from plasma sample concentrations; samples will be obtained from each randomized subject at weekly intervals during the CRT treatment period.

Data Analysis:

Efficacy Analyses

Full details of the statistical methodology for summary and analyses of the data collected in this study will be prepared separately from this protocol in a Statistical Analysis Plan (SAP).

The primary efficacy objective is to evaluate brilacidin compared to placebo in reducing the incidence of severe OM (defined as grade 3 or 4 on the WHO Oral Mucositis scale, WHO Grade ≥ 3) in subjects with HNC receiving concomitant chemoradiation therapy and a cumulative radiation dose of at least 55 Gy. For this comparison the Fishers Exact Test will be used.

Time to onset of severe OM (WHO Grade ≥ 3) will be assessed using the log rank test. Both a scale of days, and a scale of cumulative radiation dose delivered (Gy) will be used for the

Kaplan-Meier analysis. The log rank test will be used to compare treatment groups at time of onset of severe OM. Time to onset of ulcerative OM (WHO Grade ≥ 2) will be explored similarly.

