Duration of severe OM (WHO Grade ≥ 3) is evaluated two different ways: (1) Initial instance duration of severe OM is defined as the number of days from initial WHO Grade ≥ 3 during radiation therapy until the first WHO Grade 2 or lower OM Grade occurs; (2) Overall duration of severe OM is defined as the number of days from initial WHO Grade ≥ 3 during radiation therapy to the last WHO Grade ≥ 3 assessment during/after radiation therapy. If any subject does not experience severe OM, his/her duration will be set to 0. Subjects who experience severe OM but do not resolve to WHO Grade 2 or lower will be censored at the last study visit. The effect of treatment on the duration of severe OM will be assessed using a log rank statistic. Analyses will be done using both a scale of days, and a scale of cumulative radiation dose delivered (Gy).

Safety Analysis

All safety data, demographic and baseline characteristics will be summarized descriptively through appropriate data tabulations, descriptive statistics, and categorical summaries.

Changes in blood pressure, heart rate, and hematology and clinical chemistry parameters from baseline to the end of the study will be summarized. Treatment-emergent changes from values within normal range to abnormal values in clinical laboratory parameters will be identified by means of summary and shift tables. ECOG and body weight changes from baseline to the end of the study will also be summarized.

Interim Analysis

Ad-hoc interim analyses may be conducted to support decision making concerning the current clinical study, the Sponsor's clinical development projects in general or in case of any safety concerns. Such analyses may be unblinded, and the details will be documented in the SAP.

Sample Size

The proportion of subjects experiencing severe OM (WHO Grade ≥ 3) after a total cumulative radiation dose of at least 55 Gy (and no more than 72 Gy) is unknown but expected to be approximately 75% for the placebo oral rinse treatment group, and the assumption for the active Brilacidin oral rinse treatment group is estimated to reduce to approximately 35-40%. Based on these assumptions, a sample size of 23-30 subjects per treatment group is appropriate to detect the specified difference with at least 80% power.

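### The claim of at least 80% power for 23-30 per group omits alpha, sidedness and sizing method; if the planned Fisher's test is two-sided at 5%, power is about 72% at each matched end

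*Combined protocol and SAP*

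**What the plan says.** Sample Size (Protocol Synopsis) gives a severe mucositis rate "expected to be approximately 75% for the placebo oral rinse treatment group" and, for brilacidin, one "estimated to reduce to approximately 35-40" per cent. It concludes that "a sample size of 23-30 subjects per treatment group is appropriate to detect the specified difference with at least 80% power".

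Efficacy Analyses names the primary test: "For this comparison the Fishers Exact Test will be used". Number of Subjects Planned gives "Approximately 60 subjects with head and neck cancer receiving concurrent chemotherapy and radiotherapy", and Design and Methodology sets 1:1 allocation, so the plan is for about 30 per group.

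The text supplied states no significance level, no sidedness, no method for the sample size and no allowance for subjects who cannot be evaluated. Efficacy Analyses leaves full statistical detail to a separate SAP.

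**The concern.** A power figure can be checked only once the test, its level and its sidedness are known. Here only the test is given. Fisher's exact test is conservative at this size: its actual type I error lies below the nominal level, so it needs more subjects than the usual approximate formulas suggest. A size taken from such a formula will therefore look adequate and still fall short under the planned analysis.

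What is at stake is how a negative result would be read. With a stated power of at least 80%, the sponsor would take the chance of missing the assumed effect to be at most one in five. If the test is two-sided at 5% and the true active rate is 40%, that chance at 30 per group is 28% (100 - 71.9 = 28.1).

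**Working it through.** **Inputs.** Placebo rate 0.75, active rate 0.35 to 0.40, 23 to 30 per group and 80% power (Sample Size); Fisher's exact test (Efficacy Analyses); 1:1 allocation and about 60 subjects (Design and Methodology; Number of Subjects Planned). Assumed, because not stated: a 5% level, tried both one-sided and two-sided.

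**Pairing.** The natural reading matches 23 per group with 35% and 30 per group with 40%.

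**Step 1: reproduce 23-30.** Two routes give exactly these sizes.

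- *One-sided 5% Fisher.* Exact power is the sum, over all outcomes x and y, of Bin(x; n, 0.75) × Bin(y; n, p), counting only outcomes with Fisher p ≤ 0.05. For p = 0.35 it is 78.1% at n = 22 and 81.1% at n = 23. For p = 0.40 it is 78.5% at n = 29 and 80.6% at n = 30. The smallest sizes reaching 80% are 23 and 30.
- *Two-sided 5% arcsine formula.* n = 2[(1.960 + 0.842)/h]², with h = 2·arcsin√0.75 − 2·arcsin√p.
  - p = 0.35: h = 2.0944 − 1.2661 = 0.8283, so n = 22.88, rounded up to 23.
  - p = 0.40: h = 2.0944 − 1.3694 = 0.7250, so n = 29.87, rounded up to 30.

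The two-sided pooled-variance formula without continuity correction comes close, at 23.07 and 30.11. The exact power of an uncorrected two-sided chi-square test is 81.1% (23 per group, 35%) and 80.2% (30 per group, 40%).

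**Step 2: the named test at two-sided 5%.** The same enumeration with the two-sided Fisher p-value gives:

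- 23 per group, 75% v 35%: 71.6%
- 30 per group, 75% v 40%: 71.9%

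**Step 3: size needed for 80% at two-sided 5%.** For 35%, n = 28 gives 79.8% and n = 29 gives 81.7%. For 40%, n = 36 gives 79.7% and n = 37 gives 81.5%. So 29 to 37 evaluable subjects per group are needed.

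**Step 4: the planned trial, and a sensitivity case.** The case of 27 per group is 30 × 0.90. The 10% loss is an assumption; the plan gives no loss rate.

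| Exact Fisher power | 75% v 35% | 75% v 37.5% | 75% v 40% |
|---|---|---|---|
| 30 per group, two-sided 5% | 84.1% | 78.4% | 71.9% |
| 30 per group, one-sided 5% | 89.9% | 85.7% | 80.6% |
| 27 per group, two-sided 5% | 77.3% | 71.4% | 64.9% |
| 27 per group, one-sided 5% | 87.2% | 83.0% | 78.0% |

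**The case against.** The strongest reply is that the shortfall depends on a level and sidedness that the text does not state. The synopsis defers detail to a separate SAP, which may supply them, and under a one-sided 5% Fisher's test the sentence is true at both matched ends. That stands, and it is why the finding is conditional. It does not rescue the sentence as written: the synopsis makes a definite numerical claim and omits what is needed to verify it.

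It is also fair to say that this is a Phase 2 trial with rates described as approximate, and that at the planned 30 per group two-sided power does reach 84% if the active rate is 35%. That too stands, and the replacement text should show it.

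Four stronger readings are tempting, and the documents do not support them.

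- A reader might infer that a one-sided test was intended, because 23 and 30 are its exact thresholds. The two-sided arcsine formula gives the same two numbers, so a sizing formula that does not match Fisher's test explains them equally well.
- A reader might infer that the trial as a whole has 72% power. That figure belongs to the two matched pairings; at 30 per group the two-sided range is 72% to 84%.
- A reader might infer that losing any subject breaks the one-sided claim. Exact power is saw-toothed. With one subject lost from one arm only, one-sided power for 75% v 40% is 82% to 83%, and for 75% v 35% starting from 23 per group it stays at 80% to 81%. Losing one from each arm takes it just below 80% (78.5% at 29 per group; 78.1% at 22).
- A reader might apply 23 per group to the 40% rate. The range does not read that way, and about 60 subjects are planned.

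**Conclusion.** The point holds in conditional form. The power statement cannot be verified as it stands, and at the conventional two-sided 5% level the named test falls about 8 percentage points short of 80% at each matched end. Either the test is one-sided at 5% and this is not declared, or the size came from an approximate two-sided calculation that does not match the planned analysis. The documents do not decide between these, and both need correcting.

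This rests on the plan's own rates, equal groups with every subject evaluable, and an assumed 5% level. It concerns the stated power, not the choice of test or the number of patients.

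**What to change.** Keep about 60 subjects. In Efficacy Analyses, and in the SAP, state the significance level and sidedness of the primary Fisher's test. In Sample Size, name the method and replace the power sentence with exact figures for 30 evaluable subjects per group:

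- if two-sided 5%: 84% power for 75% v 35%, 78% for 75% v 37.5% and 72% for 75% v 40%;
- if one-sided 5% is intended: declare it, and quote 90% for 75% v 35% and 81% for 75% v 40%.

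Power at smaller evaluable numbers can be added as a sensitivity range, for example 27 per group: 77% and 65% two-sided, or 87% and 78% one-sided, for active rates of 35% and 40%. Label the loss rate behind it as an assumption and do not write it in as a planned figure.

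The cost is one paragraph of wording and, if the test is two-sided, a less favourable stated power. No extra patients are needed.
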